17.3 Sample Size and Power

Outcomes for patients with MRD following intensive chemotherapy at FHCRC since 2008 were reviewed. From these observed data, we fit piecewise exponential survival distributions and used these as the assumed-true distributions for the two arms. These assumed-true distributions are shown

in the figure below. From the observed data, the hazard of death was estimated to be 0.58 (transplant vs chemotherapy).

Estimates of power for specified sample sizes were obtained by randomly drawing survival times from each assumed-true survival distribution for the number of patients assumed for each group, resulting in “simulated” clinical trials under the assumptions depicted in the curves above. The data from this simulated trial were then compared using the log-rank test and a p-value was generated. This process was repeated 500 times, and the proportion of simulated trials that led to a p-value less than the significance level dictated by the trial provides an estimate of power to observe a statistically significant (at a two-sided significance level) difference in survival between the two groups.

Power estimates further assumed uniform accrual over 3 years with minimum follow-up of 2 years (so the longest potential follow-up would be 5 years and the minimum potential follow-up would be 2 years).

Based on the assumptions above, the estimated power for this design is summarized below for various significance levels and 65 patients/group. Power estimated from 500 simulations. The number of events required is estimated to be 107.

Alpha=.05, power ~ 89.4%

Alpha=.10, power ~ 93.8%

Alpha=.15, power ~ 94.8%

Alpha=.20, power ~ 96.4%

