2.2.3 Eradication of MRD at FHCRC/UW

[figure not shown]
Attempts to reduce MRD in patients with AML at FHCRC/UW have been largely unsuccessful. A recent retrospective analysis by [name] found that MRD, generally present after one course of intensive initial induction, was eliminated in 10/28 patients (36%; 95% CI 19-56%) given additional intensive chemotherapy, and remained in all 21 patients given a less intense treatment as first attempt to eliminate MRD.(Appelbaum et al., 2019) Furthermore, it is unclear whether reduction of MRD will *per se* improve post HCT outcome. [name] analysis identified 16 patients subsequently transplanted (7 of 16 in CR/CRp) of whom only 2 survived longer than 1 year, with survival similar regardless of whether MRD was eliminated (7 pts) or not (9 pts) by chemotherapy.

If MRD is resistant to elimination or if its disappearance is irrelevant, it may be preferable to proceed directly to HCT despite the deleterious influence of pre-HCT MRD on post HCT outcome. [name] review found survival from the time of initial chemotherapy was longer in the 80 patients who received HCT as first treatment for MRD than in the 49 who received chemotherapy (**figure 1A**, median 13.8 mos. vs 11.6 mos., $p = 0.01$). Survival was not statistically different in the 16/49 patients who received HCT after first receiving chemotherapy than in the 80 patients who received HCT as first therapy for MRD despite the “guarantee time” the 16 enjoyed. Furthermore, survival dated from HCT was shorter in the 16/49 patients who received chemotherapy followed by transplant than in those given HCT as initial treatment for MRD (**figure 1B**, $p= 0.02$, I median 4.4 vs. 10.4 mos.) Regardless of elimination of MRD only 2 of the 16 (12.5%, 2-38%) survived longer than 1 year vs. 23 of the 80 (29%, 19-40%) given HCT without a prior attempt to eliminate MRD.

FIGURE 1. Panel A: Survival from start of initial treatment for MRD: chemotherapy 49 patients, HCT without prior effort to eliminate MRD 80 patients, no treatment 84 patients. **Panel B:** Survival from HCT in 16 patients who received chemotherapy to eliminate pre-HCT MRD and in 78 patients who went directly to HCT (no prior attempt to reduce MRD)

A)

B)

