17.2 Primary/Secondary Endpoints, Objectives and Analytical Methods

The primary endpoint of the study is overall survival from the time of randomization. The survival (in days) of subjects in the two arms will be compared using the stratified log-rank test (stratified on number of chemotherapy cycles and disease risk, factors that randomization is stratified on). Patients still alive at last contact will be censored. End of study will be defined as 2 years after the last patient is randomized. The primary endpoint will be compared between groups using the intent-to-treat principle.

A secondary endpoint of the study is **relapse-free survival** (RFS) from the time of randomization, to be compared between groups with the stratified log-rank test. For descriptive purposes, we shall also report survival and RFS estimates from time of transplant among patients who receive a transplant. Patients alive without relapse at last contact will be censored for RFS.

[figure not shown]
A secondary objective of the study is to compare the **rate of transplantation** among patients with MRD following intensive chemotherapy. The proportion of patients who were transplanted will be compared between arms using the chi-square test

A secondary objective of the study is to examine the **types of transplant** received following treatment with CPX-351 as compared to patients receiving immediate transplantation. Among patients receiving transplantation, the proportion of patients in each arm receiving myeloablative transplant conditioning will be compared using the chi-square or Fisher's exact test. Among patients receiving transplantation, the proportion of receiving donor stem cells from a haploidentical donor, an unrelated donor, or from cord blood unit will be compared across arms using the chi-square or Fisher's exact test.

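### The 89.4% power makes no allowance for Arm A patients who never reach transplant, and its planning curves appear to be grouped by treatment received

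*Combined protocol and SAP*

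**What the plan says.** Section 17.3 reviews the centre's MRD patients since 2008 and explains that "we fit piecewise exponential survival distributions and used these as the assumed-true distributions for the two arms". It then reports: "From the observed data, the hazard of death was estimated to be 0.58 (transplant vs chemotherapy"). Power is "summarized below for various significance levels and 65 patients/group", with 107 deaths, 3 years of uniform accrual and at least 2 years of follow-up. The tests are "at a two-sided significance level", and the leading result is "Alpha=.05, power ~ 89.4" per cent. Section 17.3 gives no group sizes, no rule for placing patients in a group, no time zero, and no allowance for Arm A patients who are not transplanted.

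The only centre series described is in section 2.2.3. Its Figure 1A caption lists "chemotherapy 49 patients, HCT without prior effort to eliminate MRD 80 patients, no treatment 84 patients". The text reports that "survival from the time of initial chemotherapy was longer in the 80 patients who received HCT as first treatment for MRD" than in the 49 given chemotherapy (medians 13.8 and 11.6 months, p = 0.01). Of those 49, 16 went on to HCT. The text dates this survival from initial chemotherapy; the caption dates it from the start of initial treatment for MRD.

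For the trial, section 17.2 measures overall survival from randomization and adds: "The primary endpoint will be compared between groups using the intent-to-treat principle". Section 8.2 intends Arm A conditioning to begin within 45 days of randomization. Section 17.5 reuses the planning assumptions for future patients in the conditional-power calculation.

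**The concern.** A group defined by having received HCT leaves out everyone meant for HCT who relapsed, died or became unfit while waiting. In the trial those patients count in Arm A. The chemotherapy group in 2.2.3 starts when chemotherapy starts and keeps the 49 − 16 = 33 patients who never reached HCT, so it is already close to an intention-to-treat curve for Arm B. The selection therefore favours one arm only, and the planned difference would be wider than the one the trial can observe.

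Two figures depend on this. One is the stated power. The other is the conditional power in 17.5, where a value below 20% prompts consideration of stopping for futility. Optimistic curves for future patients would raise that value and make continuation look better supported than it is.

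**Working it through.** **1. The plan's own figure.** Inputs from 17.3: hazard ratio (HR) 0.58, 107 deaths, equal arms, two-sided 0.05. Schoenfeld's formula is power = Φ(√d/2 × |ln HR| − 1.960).

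- HR 0.58: √107/2 = 5.172; 5.172 × 0.5447 = 2.817; 2.817 − 1.960 = 0.857; power 80.4%. Simulation gives 80%.
- HR needed for 89.4% at 107 deaths: exp(−2 × (1.960 + 1.248)/√107) = 0.54.
- Deaths needed for 89.4% at HR 0.58: 4 × (3.208/0.5447)² = 139, more than the 130 patients.

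Under proportional hazards the three figures do not fit together. Section 17.3 used piecewise curves, however, and these need not be proportional. For example, HR 0.58 after a 45-day stretch without deaths in the transplant arm gives 89.4% with 106 deaths. So 89.4% is not shown to be wrong on this ground, and the illustration below starts from both 0.54 and 0.58.

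**2. Do the 17.3 curves come from the 2.2.3 series?** This is not stated, but the numbers are compatible.

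- With an 80/49 split, p = 0.01 (z = 2.576) corresponds to HR 0.58 at (2.576/0.5447)² / (80/129 × 49/129) = about 95 deaths among 129 patients.
- With uniform accrual over 3 years and follow-up of 2 to 5 years, expected deaths per arm are 65 × {1 − [exp(−2λ) − exp(−5λ)]/(3λ)}. An 11.6-month chemotherapy median gives λ = 0.717 per year and 58.6 deaths. At HR 0.58 the other arm has 48.8. The total is about 107.

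Against this, the ratio of the two medians is 11.6/13.8 = 0.84. If these are the curves, hazards are clearly not proportional.

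**3. Effect of untransplanted Arm A patients.** Assumptions: exponential survival; λ for Arm B set so that 107 deaths are expected when all of Arm A is transplanted (median 11.2 months at HR 0.54, 11.8 at HR 0.58); log-rank test; 20,000 simulated trials per cell. A fraction f of Arm A is never transplanted. The documents give neither f nor the death rate of such patients, so both are varied.

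| Starting point and assumption | f = 0 | 10% | 20% | 30% |
|---|---|---|---|---|
| HR 0.54, untransplanted die at the chemotherapy rate | 89% | 82% | 73% | 62% |
| HR 0.58, same | 80% | 72% | 63% | 52% |
| HR 0.54, same, transplant curve dated from HCT, so a 45-day death-free wait is added | 95% | 90% | 83% | 73% |
| HR 0.54, untransplanted die at twice the chemotherapy rate, no wait | 89% | 75% | 54% | 32% |

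Expected deaths stay between about 106 and 112. Repeat runs moved entries by no more than about 2 points.

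**4. Is 10 to 30% a sensible range to test?** Section 2.2.2 cites an 80% one-year relapse probability in remission with MRD without HCT. At a constant rate (an assumption), −ln 0.20 = 1.609 per year, and 1 − exp(−1.609 × 45/365.25) = 18% relapse by day 45. This is not a non-transplant rate, since some relapsed patients may still be transplanted, but it shows that losses before HCT cannot be taken as zero.

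**The case against.** **The link to 2.2.3 is inferred.** Section 17.3 does not cite that series, and its figure is not available in the text. This stands. It limits the point to a probable mismatch, and it is itself a reason to state the grouping rule and time zero.

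**The direction is not certain.** If the transplant curve was dated from HCT, the trial adds waiting time that transplanted patients survive by definition. The third row of the table shows about 90% at 10% untransplanted, essentially the stated figure. This also stands, although at 20% and 30% the loss exceeds the offset.

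**Entry criteria limit attrition.** Patients need an identified donor (3.3), and eligibility for transplant, fitness, intent to complete treatment and a caregiver (5.2). Section 5.3 excludes organ dysfunction likely to preclude safe transplant. These should keep the untransplanted share low, but no expected rate is given.

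**Futility is only partly affected.** The assumed curves apply to future patients only, observed data enter as they are, and the 20% threshold prompts a discussion rather than a stop.

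Two stronger readings are tempting and not supported. A reader might subtract the HCT group's medians, 13.8 months in the text of 2.2.3 and 10.4 months from HCT, and infer 3.4 months of guaranteed survival. A difference of medians is not a lead time, the two panels list 80 and 78 patients, and under the caption's time zero the HCT group has no such lead. A reader might also take 84/(84 + 80) = 51% as an upper bound on Arm A attrition. Nothing says those 84 untreated patients were meant for HCT.

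**Conclusion.** The point holds in a limited form. The trial analyses Arm A by intention to treat from randomization. The planning curves come from observational transplant and chemotherapy outcomes, the only described grouping conditions on reaching HCT, and 17.3 allows nothing for Arm A patients who do not reach it. The stated 89.4% is therefore likely optimistic.

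The size is not determined by the documents. It rests on an assumed untransplanted share, an assumed death rate for those patients, exponential survival, and the unstated time zero. Under the simplest assumptions, 10% untransplanted costs 7 to 8 points of power and 20% costs 16 to 17 points. Dating from HCT softens this; a higher death rate among untransplanted patients worsens it. The documents do not support saying that 89.4% is wrong, or that 17.3 certainly used treatment-received groups.

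**What to change.** In 17.3, state the grouping rule, group sizes and time zero of the two curves. Build the Arm A curve from the decision point, meaning MRD identification with HCT as the plan, and include patients who never reached HCT. Use the same time zero for both arms. Do not enter patients at HCT by delayed entry, because that conditions again on reaching it. Rerun the simulation and restate power.

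If patients planned for HCT cannot be identified in the records, state power with 10%, 20% and 30% of Arm A untransplanted, and give the death rate assumed for them. Use the same revised curves for future patients in the 17.5 conditional power.

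The cost is some re-analysis of data the centre already holds, a rerun of the simulation, and probably a less favourable stated power. No change in sample size or in the primary analysis is proposed.

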3.0 OVERVIEW OF CLINICAL TRIAL

3.1 Study Objectives

3.1.1 Primary Objectives

To determine whether treatment with CPX-351 improves overall survival over immediate alloHCT among patients with MRD following intensive chemotherapy.

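### Section 17.3's 89.4% power and 107 events describe showing that the CPX-351 arm is worse; no power is given for the primary objective that CPX-351 improves survival

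*Combined protocol and SAP*

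**What the plan says.** Section 3.1.1 gives the primary objective a direction: "To determine whether treatment with CPX-351 improves overall survival over immediate alloHCT among patients with MRD following intensive chemotherapy".

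Section 17.3 gives the only power figures. From institutional outcomes since 2008, "we fit piecewise exponential survival distributions and used these as the assumed-true distributions for the two arms". The relative effect in those data is that "the hazard of death was estimated to be 0.58 (transplant vs chemotherapy"). Trials with 65 patients per group, 3 years of uniform accrual and 2 years of minimum follow-up were simulated 500 times, and power is the chance of a "statistically significant (at a two-sided significance level) difference in survival between the two groups". The result is "Alpha=.05, power ~ 89.4" per cent, with 107 events described as required.

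Section 2.2.3 shows the same direction in the institution's own review: "survival from the time of initial chemotherapy was longer in the 80 patients who received HCT as first treatment for MRD" than in the 49 given chemotherapy ("median 13.8 mos. vs 11.6 mos"). Measured from HCT, chemotherapy followed by transplant did worse than HCT first ("median 4.4 vs. 10.4 mos").

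Section 17.2 ends the study 2 years after the last randomization. The end is set by calendar time, not by the number of deaths.

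**The concern.** The objective asks about benefit, while the simulated trials assume harm. If the chemotherapy curve stands for Arm B, nearly every significant simulated result says that CPX-351 first is worse. A reader of 17.3 would still take 89.4% as the chance of meeting the primary objective if CPX-351 works.

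The two directions need not have equal power. Log-rank power depends on the number of deaths, and the analysis time is fixed. In the harm scenario Arm B adds deaths to the transplant curve; in the benefit scenario it removes them. The trial would therefore have less power for the objective than the stated figure suggests, and a non-significant result could be read as stronger evidence against benefit than it is. Section 17.5 also reuses the same assumptions for its conditional-power look. I have not quantified that, and the point does not rest on it.

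**Working it through.** **Inputs.** From 17.3: HR 0.58 (transplant vs chemotherapy), 65 per arm, accrual 3 years, minimum follow-up 2 years, two-sided alpha 0.05, 107 events. From 2.2.3: HCT-first medians of 13.8 months (from initial chemotherapy) and 10.4 months (from HCT). My assumptions: exponential survival, because the figure with the fitted curves is not visible, and no dropout, because no rate is given.

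**Formulas.** Probability of death by the cut-off for yearly hazard λ: p(λ) = 1 − [exp(−2λ) − exp(−5λ)]/(3λ). Expected deaths: d = 65 × (p_A + p_B). Power: Φ(|ln HR| × √d / 2 − 1.960).

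**1. The plan's own figure.** With HR 0.58 and d = 107: 0.5447 × 10.344 / 2 = 2.817; 2.817 − 1.960 = 0.857; power 80.4%, not 89.4%. At alpha 0.10, 0.15 and 0.20 the formula gives 88.0%, 91.6% and 93.8%, against 93.8%, 94.8% and 96.4% stated. Simulation error is too small to explain the first gap: √(0.894 × 0.106 / 500) = 1.4 points. Under proportional hazards, 89.4% with 107 deaths implies an HR of about 0.538. Non-proportional piecewise curves could also explain it.

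**2. Reversing the effect, calibrated to 107 deaths.** Solve for the Arm A hazard that gives 107 deaths when λ_B = λ_A/0.58.
- Harm: λ_A = 0.4104 (median 20.3 months), p_A = 0.7469; λ_B = 0.7075 (median 11.8 months), p_B = 0.8993. d = 65 × 1.6462 = 107.0.
- Benefit: Arm A unchanged; λ_B = 0.58 × 0.4104 = 0.2380, p_B = 0.5560. d = 65 × 1.3029 = 84.7. Power: 0.5447 × 9.203 / 2 − 1.960 = 0.546, giving 70.8%.

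**3. Other baselines.**

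| HR | Arm A median (months) | Harm: deaths, power | Benefit: deaths, power | Loss (points) |
|---|---|---|---|---|
| 0.58 | 20.3 (calibrated to 107) | 107, 80.4% | 85, 70.8% | about 10 |
| 0.58 | 13.8 | 118.5, 84.3% | 101, 78.1% | about 6 |
| 0.58 | 10.4 | 124, 85.8% | 111, 81.9% | about 4 |
| 0.538 | 20.9 (calibrated to 107) | 107, 89.4% | 82, 80.0% | about 9 |

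If accrual runs at the 30 patients a year of section 3.4 (130/30 = 4.33 years), benefit-direction power at HR 0.58 is 74%, 80% and 83% for the three medians.

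**4. Smaller benefits (3-year accrual).** For Arm A medians of 20.3, 13.8 and 10.4 months:
- HR 0.65: 52%, 59% and 63%.
- HR 0.70: 39%, 45% and 48%.

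**5. Shape.** Log-rank simulation with proportional piecewise hazards at HR 0.58, calibrated to 107 deaths, gave 80.0% for harm and 70.1% for benefit. No significant result in the harm scenario favoured CPX-351. Two illustrative non-proportional shapes with the effect concentrated early, also calibrated to 107, gave about 88% for harm and 60% or 70% for benefit. The 4 to 10 point range therefore belongs to proportional hazards.

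**The case against.** The strongest reply is that the test is two-sided and sections 2.2.3 and 3.3 set up a comparison of two strategies. Whether chemotherapy first does harm is a real motivating question, and powering on the only contrast the institution has observed is defensible. This stands. A reader might infer that 89.4% has no bearing on the trial's question, or that the trial cannot show benefit; the documents support neither. Swapping the two curves would even keep 89.4%, but immediate transplant would then have to do as badly as historical chemotherapy, which the plan does not assume.

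A reader might also infer a fall from 89.4% to about 70%. That mixes two gaps: roughly half of it is the separate failure of HR 0.58 with 107 events to give 89.4% under proportional hazards. Nor does this show that 89.4% is wrong, since the fitted curves are not visible.

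The baseline is uncertain too. The 20.3-month median implies 66% alive at 1 year, whereas 2.2.3 reports 23 of 80 (29%) surviving beyond 1 year and 2.2.2 cites 30-40%. The 107 may also be a formula result and not a simulated death count: HR 0.58 at 80% power needs 106 events. If so, calibrating to it has no basis. On the 13.8- and 10.4-month medians the loss is only 4 to 6 points, and at 10.4 months the benefit scenario yields 111 deaths. It is therefore not generally true that 107 deaths would not be reached.

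**Conclusion.** The point holds as a reporting gap in 17.3. The stated power and event count come from a scenario in which the CPX-351 arm is worse, and nothing is stated for the direction named in the primary objective. That follows from the text and needs no modelling, given the natural reading that the chemotherapy curve stands for Arm B.

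The size is less certain. With exponential curves, no dropout and the plan's accrual and follow-up, reversing the same relative effect costs about 4 to 10 points. Power for benefit at HR 0.58 is about 71% to 82%, and for HR 0.65 to 0.70 about 39% to 63%. Non-proportional curves could make the loss larger.

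The test, endpoint, analysis time and sample size are unaffected, so this should be fixed but is not a fatal flaw.

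**What to change.** In section 17.3, re-run the existing simulation with Arm A on the fitted transplant curve and Arm B at HR 0.58 relative to Arm A, and also at smaller benefits such as 0.65 and 0.70 (illustrative values, not from the plan). Report expected deaths and power for each as the power for the primary objective. Label 89.4% and 107 events as applying to detection of inferiority of the CPX-351 arm. In the same table, state whether 107 is the simulated number of deaths or a formula result, and how 89.4% arises from HR 0.58.

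Keep n = 130. The cost is one re-run of existing code, a revised table and a less favourable stated power.

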17.4 Randomization

Subject randomization will be 1:1 and will be done using a permuted-block routine with random block sizes. Randomization will be stratified on two factors: number of chemotherapy cycles (1 vs. 2 courses pre-HCT) and disease risk (standard risk vs. high risk, where high-risk disease is defined based on ELN or being in CRi).

17.5 Study-suspension Rules and Interim Futility Analysis

As noted above in section 11, the CPX arm will be followed carefully for toxicity and the inability for patients treated with CPX to proceed to HCT or be delayed to HCT (defined as start of transplant conditioning regimen more than 60 days following the start of CPX; inability to receive HCT or a delayed HCT is defined below as “failure”) due to toxicity attributable to CPX. Toxicity attributable to CPX will be defined as any adverse event that is possibly, probably, or definitely related to CPX. Events that do not meet this definition but result in the delay of HCT or inability to proceed to HCT (e.g.

treating clinic logistics, scheduling, donor availability, unrelated adverse events) will not count toward study-suspension rules but will be captured as protocol deviations in the study records. In situations where HCT is delayed or patient is unable to proceed due to toxicity and attribution to CPX is unclear, the DSMB will be consulted.

If toxicity from CPX leads to an observed failure rate of 20% or more, the study will be suspended pending review by the DSMB. This assessment will be made after every 5th enrolled patient, so any of the following would trigger this suspension rule: 1 of 5 or fewer, 2 of 10 or fewer, 3 of 15 or fewer, 4 of 20 or fewer, 5 of 25 or fewer, 6 of 30 or fewer, 7 of 35 or fewer, 8 of 40 or fewer, 9 of 45 or fewer, 10 of 50 or fewer, 11 of 55 or fewer, 12 of 60 or fewer, or 13 of 65 or fewer patients experience a failure.

After 65 patients have been enrolled and minimum follow-up reaches 6 months, the conditional power (given results up to this point) to reach a statistically significant difference at the end of the study will be calculated under the assumptions (for patients to be enrolled in the future) used in the initial power calculations. If this conditional power is less than 20%, consideration will be given to terminating the study due to futility. Other considerations will go into this decision (not just the conditional power) and presented to the DSMB, but this will be a large driver of the ultimate decision. Accrual to the study will not be suspended while the interim analysis is being conducted.

**Projected Target Accrual
ETHNIC AND GENDER DISTRIBUTION CHART**

TARGETED / PLANNED ENROLLMENT: 130			
Ethnic Category	Sex / Gender		
	Females	Males	Total
Hispanic or Latino	1	3	4
Not Hispanic or Latino	55	71	126
Ethnic Category Total of All Subjects*	56	74	130
Racial Categories			
American Indian / Alaska Native	1	3	4
Asian	5	3	8
Native Hawaiian or Other Pacific	0	0	0
Black or African American	1	2	3
White	42	58	100
More Than One Race	7	8	15
Racial Categories: Total of All Subjects*	56	74	130

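### The futility conditional power in 17.5 assumes transplant is better and names no direction, so it can fall below 20% because CPX-351 is ahead

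*Combined protocol and SAP*

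**What the plan says.** The primary objective (3.1.1) is "To determine whether treatment with CPX-351 improves overall survival over immediate alloHCT" in patients with MRD.

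Section 17.3 takes its planning curves from a retrospective institutional series, in which "the hazard of death was estimated to be 0.58 (transplant vs chemotherapy". It gives no curve or effect size in which CPX-351 is the better arm. Power is the chance of a "statistically significant (at a two-sided significance level) difference in survival between the two groups", tabulated at four alpha levels (0.05, 0.10, 0.15, 0.20), with 107 deaths expected from 130 patients.

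Section 17.5 plans one look, once 65 patients are enrolled with at least 6 months of follow-up. The quantity is "the conditional power (given results up to this point) to reach a statistically significant difference at the end of the study", which "will be calculated under the assumptions (for patients to be enrolled in the future) used in the initial power calculations". Then: "If this conditional power is less than 20%, consideration will be given to terminating the study due to futility". The text adds: "Other considerations will go into this decision (not just the conditional power) and presented to the DSMB, but this will be a large driver". It also says: "Accrual to the study will not be suspended while the interim analysis is being conducted".

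**The concern.** CP under a design assumption is a routine futility tool when that assumption points the way the trial hopes to conclude. Here it points the other way. Patients still to be enrolled are projected to do better on immediate transplant. If transplant leads at the interim, the projection adds to the lead and CP is high. If CPX-351 leads, the projection cancels the lead and CP falls. Section 17.5 attaches the word futility to the low value whatever caused it.

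This is the only planned interim survival analysis. Nothing in 17.5 tells the DSMB that a value below 20% may reflect a lead for the arm named in the objective rather than little prospect of showing any difference.

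**Working it through.** **Inputs.** From 17.3: hazard 0.58, 107 deaths, two-sided test, alpha 0.05 to 0.20. From 17.4: 1:1 allocation. From 17.5: the 20% threshold. Assumed, because the plan gives no figure: 37 deaths at the interim, varied below.

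**The plan's own power.** With drift θ = |ln 0.58| × √107 / 2 = 0.545 × 10.34 / 2 = 2.82, power at alpha 0.05 is Φ(2.82 − 1.96) = 80.4%, against the stated 89.4%. This gap is not called an error: the planning curves are piecewise exponential, their figure is not shown, and they may not be proportional. The drift that matches 89.4% is 1.96 + 1.25 = 3.21, so both values were used.

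**Formula.** Let t = deaths/107, HR = CPX-351/transplant, and Z = ln(HR) × √deaths / 2, positive when transplant leads. Given Z, the final statistic is normal with mean Z√t + θ(1 − t) and variance 1 − t. CP as written is the probability of ending beyond +1.96 or −1.96. This puts the planning drift on all remaining data, which is looser than 17.5, where the assumption is stated only for patients yet to be enrolled.

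**Worked case, observed HR 0.58.** t = 37/107 = 0.346; Z = −0.545 × 6.08 / 2 = −1.66; Z√t = −0.974; θ(1 − t) = 1.843; mean = 0.869; SD = 0.809.
- Transplant significant: P(N > (1.96 − 0.869)/0.809 = 1.35) = 8.9%. CPX-351 significant: about 0.02%. CP as written is 8.9%.
- Mirrored drift (−2.82): mean = −0.974 − 1.843 = −2.817. CPX-351 significant: Φ((2.817 − 1.96)/0.809 = 1.06) = 85.5%.

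| Observed HR (CPX-351/transplant) | CP as written | CP, CPX-351 win, mirrored drift | CP, CPX-351 win, observed trend |
|---|---|---|---|
| 1.72 | 85% | 9% | 0% |
| 1.00 | 44% | 44% | 1% |
| 0.80 | 26% | 64% | 16% |
| 0.70 | 18% | 74% | 44% |
| 0.58 | 9% | 86% | 86% |

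**Flagged range.** At alpha 0.05, CP is below 20% for observed HR from about 0.17 to 0.73. At alpha 0.20 the range is 0.26 to 0.49, so HR 0.58 is not flagged there (CP 31%). Across 30 to 45 deaths, both drifts and all four alphas, the highest flagged HR runs from 0.29 to 0.87 and never reaches 1. With more deaths it moves towards 1: at 54 deaths, drift 2.82 and alpha 0.05, it is 0.99.

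**A reading closer to the text.** Here planning hazards apply only to patients not yet enrolled, and enrolled patients continue at the observed arm rates. This was simulated with assumed exponential curves (medians 20.3 months transplant, 11.8 months CPX-351, calibrated to 107 deaths of 130) at alpha 0.05. Between 51% and 66% of trials were flagged at true HR 0.58, and 55–59% at true HR 1.0. Among flagged trials, the observed HR lay between 0.8 and 1.25 in 26–32% at true HR 0.58 and in 58–69% at true HR 1.0. Most flags still had CPX-351 numerically ahead in both cases, but often by little.

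**The case against.** Two-sided CP is a well-defined quantity that matches a two-sided test, and section 2.2.3 openly allows that going straight to transplant may be preferable. Planning on a transplant advantage is therefore deliberate. A high CP when transplant leads is consistent with this and is not faulted. What the two-sided test does not settle is how a low value should be read when CPX-351 leads.

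The rule is also advisory, and other considerations go to the DSMB. A reader might infer that the DSMB would see the low CP without knowing which arm leads, or that a CPX-351 lead would stop the trial. The documents say neither. Advisory status limits the harm, but the rule as written still produces a misleading number and gives it heavy weight.

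The strongest objection concerns size. On the closer reading, flag rates barely separate a true CPX-351 benefit from no difference, and many flags come from interim results near HR 1, where low CP is ordinary futility. A numerical lead is only the sign of the log-rank statistic and can be trivial. This stands, and it rules out a claim that most flags reflect a meaningful CPX-351 advantage.

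**Conclusion.** The point holds as a matter of direction. Under 17.5 as written, an interim CPX-351 lead lowers CP and can take it below the futility threshold, although 3.1.1 asks whether CPX-351 is better. In the illustration the same interim result gives about 9% or about 86%, depending on which arm the design assumption favours and which arm must win.

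Those figures rest on 37 assumed deaths, planning drift on all remaining data, and alpha 0.05. A reader might infer from the flagged range that a low CP always means CPX-351 is ahead. That follows only if the planning hazards also govern further follow-up of enrolled patients, which 17.5 does not say. The share of flags caused by a meaningful CPX-351 lead cannot be fixed from the documents: the final alpha, the interim deaths, the planning curves and the hazards for enrolled patients are all unstated or not shown. The matter should be fixed; because the rule is advisory, it does not invalidate the design.

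**What to change.** In 17.5:

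1. Report CP separately for each direction. For CPX-351 superiority, use a pre-specified CPX-351-benefit assumption and also the observed trend. Label the former a design assumption, since the documents give no survival estimate for CPX-351 in MRD. For transplant superiority, use the 17.3 assumption. Give the DSMB these values with the interim hazard ratio.
2. State that CP below 20% under the transplant-favouring assumption is not by itself a futility signal when the interim estimate favours CPX-351.
3. Name the final alpha and the hazards used for further follow-up of patients already enrolled. CP cannot be computed reproducibly without them, whichever direction is used.

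The cost is a few sentences, one extra calculation on the same data, no extra patients, and fewer automatic flags. Whether futility should require both directions to be below 20% is the sponsor's choice, and its operating characteristics should be stated. In the simulation on the closer reading, with a mirrored CPX-351-benefit assumption, that rule fired in 12–28% of trials with no true difference at alpha 0.05, in at most 10% at 0.10, and in about 2% or fewer at 0.15 and 0.20. At the higher alphas it would rarely act.
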